2.8.3.2 Vital signs

The following quantitative variables will be summarized: Weight (kg), Temperature (°C), Pulse (beats/min), Supine systolic blood pressure (mmHg) and Supine diastolic blood pressure (mmHg).

Analysis in vital sign measurement using descriptive summary statistics for the change from baseline for each post-baseline visit will be performed by vital sign and treatment group. Change from baseline will only be summarized for patients with both baseline and post-baseline values and will be calculated as:

$$\text{Change from baseline} = \text{post-baseline value} - \text{baseline value}$$

As body temperature is being measured using different routes, in order to harmonize all temperature values, for summaries a correction will be made to methods other than axillary as follows.

$$\text{Body temperature (axillary equivalent)} = \text{value (oral/tympanic/rectal)} - 0.5 \text{ degrees } (^\circ\text{C}).$$

The number and percentage of patients with newly occurring notable vital signs will be presented. Criteria for notable vital sign abnormalities are provided in [Table 2-4](#) below.

Table 2-4 Criteria for notable vital sign abnormalities

Vital sign (unit)	Notable abnormalities
Systolic blood pressure (mmHg) for age ≥ 18 years	≥ 180 mmHg/ ≤ 90 mmHg with increase/decrease from baseline of ≥ 20 mmHg
Systolic blood pressure (mmHg) for age < 18 years	$>$ ULN or $<$ LLN defined in Table 2-5
Diastolic blood pressure (mmHg) for age ≥ 18 years	≥ 105 mmHg/ ≤ 50 mmHg with increase/decrease from baseline of ≥ 15 mmHg
Diastolic blood pressure (mmHg) for age < 18 years	$>$ ULN or $<$ LLN defined in Table 2-5
Pulse (beats/min) for age ≥ 18 years	≥ 120 bpm/ ≤ 50 bpm with increase/decrease from baseline of ≥ 15 bpm
Pulse (beats/min) for age < 18 years	$>$ ULN or $<$ LLN defined in Table 2-3
Temperature ($^{\circ}\text{C}$)	≥ 37.5 (axillary) or ≥ 38.0 (other routes)
Weight	decrease $> 7\%$ from Baseline increase $> 7\%$ from Baseline

A listing of all newly occurring or worsening abnormalities as compared with baseline will be provided, as well as a by-patient listing of all vital signs.

Table 2-5 Normal blood pressure by age

Age (years)	Normal range systolic (mmhg)	Normal range diastolic (mmhg)
1 - ≤ 3	90-105	55-70
3 - ≤ 6	95-110	60-75
6 - ≤ 12	100-120	60-75
> 12 - < 18	110-135	65-85

[figure not shown]
Source: Nelson Textbook of Pediatrics, 18th Edition

2.9 Pharmacokinetic endpoints

PK concentrations below the limit of quantification will be treated as zero in summary statistics and for the calculation of pharmacokinetic parameters by non-compartmental analysis. Descriptive statistics of pharmacokinetic parameters will include arithmetic and geometric (means, standard deviation (SD), median, minimum and maximum, etc). In the study rich PK data will be collected from subset of patients whereas all other patient will provide sparse PK samples. A separate PK analysis will be performed for patients providing rich PK data. Parameters such as AUC_{inf}, AUC_{last}, AUC_{0-t}, C_{max} and T_{max} may be reported for the patients with rich PK data using non-compartmental method of analysis (using Phoenix 6.4 or higher). 2-sided 90% confidence intervals for AUC_{0-24h}, C_{max} and T_{max} PK parameters of KAF156 and lumefantrine will be calculated by part and treatment group using normal or log-normal approximation as applicable. Non-compartmental PK analysis for patients with sparse data will also be conducted and feasible PK parameters will be reported. A descriptive statistics for concentration at nominal time point of 168 hours post dose or any other time point identified

[figure not shown]
critical for the cure may also be reported for all the patients. These PK parameters/ PK concentration may also be explored graphically.

[figure not shown]
All the PK data may be pooled for population pharmacokinetics analysis across studies and the broad principles outlined in the Food and Drug Administration (FDA) Guidance for Industry: Population Pharmacokinetics would be followed.

[figure not shown]

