#### **Part A:**

Approximately 325 male and female adult/adolescent patients ( $\geq 12$  years old and  $\geq 35.0$  kg) will be enrolled in Part A of the study.

At screening, eligible patients will be randomized into one of the seven cohorts, i.e., six KAF156 and LUM-SDF dose combinations and a control arm (see [Figure 3-1](#)), in 2:2:2:2:2:2:1 ratios. The standard doses of KAF156 as shown below may be corrected according to [Table 3-1](#) in case of increased exposure in the PK Run-in Part (see [Appendix 5](#)).

- Cohort 1: KAF156 400 mg and LUM-SDF 960 mg once daily (QD) for 1 day
- Cohort 2: KAF156 800 mg and LUM-SDF 960 mg QD for 1 day
- Cohort 3: KAF156 400 mg and LUM-SDF 960 mg QD for 2 days
- Cohort 4: KAF156 200 mg and LUM-SDF 480 mg QD for 3 days
- Cohort 5: KAF156 400 mg and LUM-SDF 480 mg QD for 3 days
- Cohort 6: KAF156 400 mg and LUM-SDF 960 mg QD for 3 days
- Cohort 7: Coartem® twice a day (BID) for 3 days (dosing as per product label)

Patients will be admitted to the hospital on Day 1. They will be dosed on either a) Day 1 alone or b) Days 1 and 2 or c) Days 1, 2 and 3 depending on the assigned study arm, and will remain in the hospital under close supervision until they are discharged by the investigator or designee on Day 4. At the discretion of the investigator, patients may stay additional days if needed. The patients will then be followed up until Day 43. Visits to assess safety and efficacy will be scheduled during the follow-up period as described in the schedule of assessments tables ([Table 6-1](#), [Table 6-2](#), [Table 6-3](#) and [Table 6-4](#)). If malaria symptoms re-emerge outside the scheduled study visits, patients will be instructed to contact the investigator.

Rich pharmacokinetic (PK) sampling will be done in 6 patients each in cohorts 1-4 and 6, and in 12 patients in Cohort 5 (see [Table 6-3](#)), and sparse PK sampling will be done in the rest of the patients as well as in Cohort 7 (see [Table 6-4](#)).

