**Table 6-3 PK sampling schedule for patients involved in RICH PK sampling (PK Run-in Part and Part A)**

Epoch	Screen		Treatment 														Follow-up					UNS															
Visit Numbers 	1	99	101							102							199														299 End of Follow up / PSW						
			EOT Epoch / premature discontinuation														201	202	203	204	205																
Study Day			1							2							3														4	5	8	15	29	43	
Window			±0 day							±0 day							±0 day														±0 day	+1 day	±1 day	±2 day	±4 days	±4 days	
Time (post-dose) in hours	-24 to <0		0	1	3	6	8	12	18	24	27	30	36	48	51	54	60	68	72	96	168	336	672	1008													
KAF-LUM SDF 1D cohort			X 	x	x	x		x	x	x		x		x					x	x																	
KAF-LUM SDF 2D cohort			X 	x	x	x		x		x	x	x	x	x				x	x	x																	
KAF-LUM SDF 3D cohort			X 	x	x	x		x		x				x	x	x		x	x	x	x																

**Notes:** A) Each PK sample will be 1mL blood. Further details on sample collection, numbering, processing and shipment can be found in the Site Operations Manual. B) Missed PK sampling time should be taken as soon as possible and actual time should be recorded. For Scheduled time ≤ 2 h ± 10 min; 2 to < 24 h ± 30 min; ≥ 24 to 72 h ± 2 h; > 72 h ± 24 h.

UNS = Unscheduled visit

EOT = End of Treatment

[figure not shown]
PSW = Premature Study Withdrawal

X = assessment to be recorded on clinical data base

 Patients will be admitted to the hospital on Day 1 and will remain in the hospital under close supervision until they are discharged by the investigator or designee on Day 4.

 Visit structure given for internal programming purpose only.

 PK sampling at Visit 101 should be done in a range of 15 min to 1 min prior to dosing.

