### 9.5.4 Pharmacokinetics

PK concentrations below the limit of quantification will be treated as zero in summary statistics and for the calculation of pharmacokinetic parameters by non-compartmental analysis. Descriptive statistics of pharmacokinetic parameters will include arithmetic and geometric (means, standard deviation (SD), median, minimum and maximum, etc). In the study rich PK data will be collected from subset of patients whereas all other patient will provide sparse PK samples. A separate PK analysis will be performed for patients providing rich PK data. Parameters such as AUCinf, AUClast, AUC0-t, Cmax and Tmax will be reported for the patients with rich PK data using non-compartmental method of analysis (using Phoenix 6.4 or higher). For the PK Run-in cohort, 2-sided 90% confidence intervals for AUC0-24h, Cmax and Tmax PK parameters of KAF156 and lumefantrine will be calculated by part and treatment group using normal or log-normal approximation as applicable. Non-compartmental PK analysis for patients with sparse data will also be conducted and feasible PK parameters will be reported. A descriptive statistics for concentration at nominal time point of 168 hours post dose or any other time point identified critical for the cure would also be reported for all the patients.

All the PK data will be pooled for population pharmacokinetics analysis and the broad principles outlined in the Food and Drug Administration (FDA) Guidance for Industry: Population Pharmacokinetics would be followed.

[REDACTED]

[REDACTED]

[REDACTED]

[REDACTED]

[REDACTED]

[REDACTED]

[REDACTED]

[REDACTED]

[REDACTED]

[REDACTED]

[REDACTED]

[REDACTED]

[REDACTED]

[REDACTED]

[REDACTED]

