### 9.7 Interim assessments

**PK Run-in Part:** For the patients in the PK Run-in KAF156 200 mg/LUM-SDF 960 mg cohort, PK analyses will be performed on the samples collected in the first 24 hours.  $AUC_{0-24}$ , for KAF156 and lumefantrine will be calculated and compared with the expected values when one drug was given alone. Dosing in Part A will subsequently proceed according to the algorithm specified in [Table 3-1](#). 12 patients with evaluable PK data are needed in the PK Run-in cohort.

[REDACTED]

**End of Part A:** After the last patient has completed the last visit in Part A, the clinical database will be cleaned and locked.

An interim assessment will be performed to evaluate if any KAF156 and LUM-SDF combination is effective and safe and which KAF156 and LUM-SDF dose regimen(s) will be carried forward in Part B. Only the primary efficacy endpoint, selected secondary efficacy, PK, and safety endpoints (all adverse events, serious adverse events and laboratory results) will be analyzed by the study biostatistics team.

The results will be communicated to relevant internal and external people who will contribute to the selection of effective and safe dose regimen.

**DMC reports:** At selected time points during the study, DMC reports will be provided by a CRO team not involved in the study conduct. The unblinded DMC reports will be reviewed by the DMC.

Additional ad-hoc safety review may be requested by DMC or Novartis if needed. Only the decision or information needed for planning/modifying the trial (such as continuation of study, dosing information for new patients, etc.) will be communicated to the blind clinical trial team involved in trial conduct. No further dissemination of DMC reports should occur.

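### The normal or log-normal 90% interval for Tmax has no assured coverage, because Tmax clusters at a few sampling times and rich-PK groups have only 6 or 12 patients.

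*SAP*

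**What the plan says.** SAP 2.9 announces "2-sided 90% confidence intervals for" three parameters together, AUC0-24h, Cmax and Tmax, and then gives one method for all of them: the intervals "will be calculated by part and treatment group using normal or log-normal approximation as applicable". The closing words of that sentence choose between two approximations. They do not offer a third method for Tmax.

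Protocol 9.5.4 has the same sentence, limited at its start to the run-in: "For the PK Run-in cohort, 2-sided 90% confidence intervals for". The SAP drops that limitation, so its intervals extend to the treatment groups of Part A.

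Both sections also plan the median, minimum and maximum of the PK parameters. The sample size text (Protocol 9.8, SAP 3) argues for a log-normal distribution for AUC and Cmax only.

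The group sizes are stated. For the run-in, Protocol 9.7 says that "12 patients with evaluable PK data are needed in the PK Run-in cohort". For Part A, Protocol 3.1 says: "Rich pharmacokinetic (PK) sampling will be done in 6 patients each in cohorts 1-4 and 6, and in 12 patients in Cohort 5".

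**The concern.** A t-interval on the raw or log scale is reasonable for AUC0-24h and Cmax, which vary continuously. Tmax is the time of the highest sampled concentration, so its values gather around the few scheduled times. If most patients peak at the same sample, a group of 6 or 12 can show little or no spread, and the sample standard deviation then understates the uncertainty. An interval labelled 90% may have much lower coverage.

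What is at stake is the accuracy of one reported interval. Key PK parameters are a secondary objective and Tmax is among the listed PK assessments, but no hypothesis or decision rule uses it.

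**Working it through.** **1. The plan's own precision figure.** With t the 95th percentile of Student's t on n−1 degrees of freedom, P(half width ≤ w) = P(χ²(n−1) ≤ (n−1)·[w√n/(t·SD)]²). For n=12, t = 1.796.

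- log AUC0-24h, SD 0.26, w = 0.155: 11 × [0.155 × 3.464/(1.796 × 0.26)]² = 14.5, giving 0.796.
- log Cmax, SD 0.21, w = 0.126: the argument is 14.7, giving 0.805.

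Both agree with the stated 0.80. No precision figure is given for Tmax, only the nominal 90%.

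**2. Inputs for Tmax.**

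- Sampling times up to 24 h after the first dose (Protocol Table 6-3): 1, 3, 6, 12, 18 and 24 h in the run-in and 1-day cohorts. The 2- and 3-day cohorts omit 18 h.
- Group sizes: n = 6 and n = 12.
- Tmax distribution: not given, so assumed patterns are used and shown as a range.

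**3. One case by hand.** Assume 90% of patients peak at 3 h and 10% at 6 h, so the true mean is 3.3 h. With k of 6 patients at 6 h, the mean is 3 + 0.5k, the SD is 3√[k(6−k)/30] and the interval is mean ± 2.015·SD/√6.

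| k | Probability | Interval (h) | Contains 3.3? |
|---|---|---|---|
| 0 | 0.531 | 3.00 to 3.00 | no |
| 1 | 0.354 | 2.49 to 4.51 | yes |
| 2 | 0.098 | 2.73 to 5.27 | yes |
| 3 | 0.015 | 3.15 to 5.85 | yes |
| 4 or more | 0.001 | lower limit 3.73 or above | no |

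Coverage is 0.354 + 0.098 + 0.015 = 0.467. At n=12 the interval contains 3.3 for k = 1 to 4, so coverage is 0.377 + 0.230 + 0.085 + 0.021 = 0.713.

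**4. Other patterns.** Exact coverage of the nominal 90% t-interval, by enumerating all samples:

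| Assumed Tmax pattern | n=6 | n=12 |
|---|---|---|
| 3/6 h at 0.9/0.1 | 0.467 | 0.713 |
| 1/3/6 h at 0.1/0.8/0.1 | 0.715 | 0.809 |
| 3/6 h at 0.75/0.25 | 0.817 | 0.827 |
| Equal over all six times | 0.879 | 0.898 |
| 3/6 h at 0.5/0.5 | 0.969 | 0.854 |

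The log scale gives the same coverage in the first three rows and the last. With two values it only relabels the points. In the equal pattern it gives 0.877 and 0.894. It can help when values are more spread: for 1/3/6/12 h at 0.1/0.5/0.3/0.1 the raw scale gives 0.806 and 0.858, and the log scale 0.909 and 0.904.

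**5. Actual times.** Times were simulated uniformly within the Table 6-3 windows (±10 min at 1 h, ±30 min at 3 to 18 h, ±2 h at 24 h) for seven patterns. Coverage was 0.64 to 0.92 at n=6, 0.72 to 0.91 at n=12 and 0.88 to 0.90 at n=40. For 3/6 h at 0.9/0.1 it was 0.640 (raw) and 0.789 (log) at n=6, and 0.716 and 0.775 at n=12.

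**6. The alternative.** The interval from the r-th smallest to the r-th largest value contains the median with probability at least 1 − 2·P(Bin(n, 0.5) ≤ r−1), for any distribution, discrete or not.

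- n=6, r=1: 1 − 2 × 1/64 = 0.969. The next pair inward (r=2) gives 1 − 2 × 7/64 = 0.781.
- n=12, r=3: 1 − 2 × 79/4096 = 0.961. The next pair inward (r=4) gives 1 − 2 × 299/4096 = 0.854.

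These are therefore the narrowest symmetric pairs that guarantee at least 90%.

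**The case against.** Several points on the other side stand.

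- *Coverage does not always fail.* A reader might infer that the stated 90% is simply not achieved. The documents give no Tmax distribution. Coverage is close to nominal when values are spread over many times, and exceeds it at n=6 for an even split between two.
- *Tmax need not be strictly discrete.* Table 6-3 allows sampling windows and says: "Missed PK sampling time should be taken as soon as possible and actual time should be recorded". Nothing says that Tmax is read from nominal hours. Exact ties may therefore be uncommon, but values still cluster and the shortfall remains in concentrated patterns. It largely disappears at n=40, so small groups with concentrated or skewed values are the drivers, not discreteness alone.
- *Zero width is no argument against the plan.* A reader might count it as a separate defect because the t-interval shrinks to a point when all values tie. The order-statistic interval does so at least as often, while keeping its coverage for the median.
- *The six-time schedule is not universal.* The 2- and 3-day cohorts omit 18 h and add samples after later doses, and SAP 2.9 does not confine Tmax to the first 24 h. The equal-spread pattern represents only the run-in and 1-day cohorts.
- *A sound summary is already planned.* The median, minimum and maximum will be reported. At n=6 the proposed interval is that same range with a confidence level attached.

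None of this justifies a normal or log-normal interval for Tmax.

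**Conclusion.** The point holds in a limited form. Both documents prescribe an interval for Tmax whose 90% coverage is not assured at n=6 or 12. Among the tabulated patterns, coverage runs from 0.47 to 0.97 at n=6 and from 0.71 to 0.90 at n=12. These are illustrations under assumed distributions, not bounds or predictions for this trial.

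A reader might also infer that dose selection is exposed. The documents do not support that: Protocol 3.3 and Table 3-1 base the Part A dose adaptation on AUC0-24h. The effect is confined to the PK description, and the change is desirable rather than essential.

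**What to change.** In SAP 2.9, restrict the normal or log-normal 90% intervals to AUC0-24h and Cmax. For Tmax, rely on the median, minimum and maximum already planned. If an interval is wanted, report an order-statistic interval for the median and print its attained confidence: minimum to maximum at n=6 (at least 96.9%), 3rd to 10th ordered value at n=12 (at least 96.1%). For other numbers of evaluable patients, choose the pair with the formula above. State whether Tmax uses actual or nominal times. Record the departure from Protocol 9.5.4 in SAP 4, which currently lists no changes.

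The cost is a sentence or two of text, a standard calculation and no new data. The downside is that the target moves from the mean to the median, and the confidence level exceeds 90% because no symmetric pair gives exactly that level at these sample sizes.

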2.11 Patient-reported outcomes

NA

2.14 Overview of analysis methods

An overview of statistical analyses and methods applied to efficacy variables and safety variables are given in [Table 2-6](#) and [Table 2-7](#).

Table 2-6 Overview of analysis methods for baseline data and efficacy variables

Variable(s)	Summary statistics for binary/categorical data	Listings	Between treatment comparison	95% CI for each treatment group	Summary statistics for continuous data	Time-to-event data analysis K-M	Graphs	Pooled analysis (Part A +Part B)
Medical history	X	X	-	-	-	-	-	-
Demographics and baseline characteristics	X	X	-	-	-	-	-	X
Patient disposition	X	X	-	-	-	-	-	X
Prior medication use	X	X	-	-	-	-	-	-
Concomitant medication use	X	X	-	-	-	-	-	-
Concomitant rescue medication use	X	X	-	-	-	-	-	-
Concomitant Non-study drug antimalarial medication use	X	X	-	-	-	-	-	-
Prior other prohibited medications use	X	X	-	-	-	-	-	-
Concomitant other prohibited medications use	X	X	-	-	-	-	-	-
PCR-corrected Response at Day 29	X	X	X	X	-	X	X	X
PCR-corrected response at Days 15 and 43	X	X	X	X	-	X	X	X
Uncorrected ACPR response at Days 15, 29, and 43	X	X	X	X	-	X	X	X
Proportion of patients with parasitemia at 12, 24, and 48 hours after treatment;	X	X		X	-	-	-	-
Time to parasite clearance (PCT)		X	X	-	-	X	X	X
Time to fever clearance (FCT)		X	X	-	-	X	X	X
Proportion of patients with early treatment failure	X	X	-	X	-	-	-	-

Variable(s)	Summary statistics for binary/categorical data	Listings	Between treatment comparison	95% CI for each treatment group	Summary statistics for continuous data	Time-to-event data analysis K-M	Graphs	Pooled analysis (Part A +Part B)
Proportion of patients with late clinical failure	X	X	-	X	-	-	-	-
Proportion of patients with late parasitological failure (LPF)	X	X	-	X	-	-	-	-
Incidence rate of recrudescence at Days 15, 29 and 43	X	-	-	-	-	X	X	-
Incidence rate of reinfection at Days 15, 29 and 43	X	-	-	-	-	X	X	-
Proportion of infected mosquitoes	-	-	-	-	X	-	-	-

Table 2-7 Overview of analysis methods for safety/PK variables

Variable(s)	Summary statistics for binary/categorical data	Listings	Summary statistics for continuous data	Graphs	Pooled analysis (Part A +Part B)
AE	X	X	-	-	X
SAE	X	X	-	-	X
severe malaria	X	X	-	-	
Adverse events of special interest	X	X	-	-	X
Hematology change from baseline	-	X	X	X	X
Biochemistry change from baseline	-	X	X	X	X
Liver abnormalities	X	X	-	-	X
ECG abnormality	X	X	-	-	X
Vital signs change from baseline	-	X	X	-	X
Notable vital signs abnormality	X	X	-	-	X
Drug concentrations	-	X	X	-	-

2.15 Interim analysis

PK Run-in Part: For the patients in the PK Run-in KAF156 200 mg/LUM-SDF 960 mg cohort, PK analyses will be performed on the samples collected in the first 24 hours. AUC_{0-24} , for KAF156 and lumefantrine will be calculated and compared with the expected values when one drug was given alone. Dosing in Part A will subsequently proceed according to the algorithm specified in protocol, Table 3-1.

End of Part A: After the last patient has completed the last visit in Part A, the clinical database will be cleaned and locked.

An interim assessment will be performed to evaluate if any KAF156 and LUM-SDF combination is effective and safe and which KAF156 and LUM-SDF dose regimen(s) will be carried forward in Part B. Only the primary efficacy endpoint, selected secondary efficacy (uncorrected ACPR at Day 29, PCT, and FCT), PK, and safety endpoints (all adverse events, serious adverse events and laboratory results) will be analyzed by the study biostatistics team. Other efficacy and safety endpoints will be analyzed if deemed necessary.

The results will be communicated to relevant internal and external people who will contribute to the selection of effective and safe dose regimen.

DMC reports: At selected time points during the study, DMC reports will be provided by a CRO team not involved in the study conduct. The unblinded DMC reports will be reviewed by the DMC.

Additional ad-hoc safety review may be requested by DMC or Novartis if needed. Only the decision or information needed for planning/modifying the trial (such as continuation of study, dosing information for new patients, etc.) will be communicated to the blind clinical trial team involved in trial conduct. No further dissemination of DMC reports should occur.

Below is the outline of the data required for the DMC review.

Table 2-8 Specification of data outputs for DMC data review

Output	Analysis set	Periodic safety review	End of Part A interim analysis
Baseline			
Patient disposition	Randomized	Yes	Yes
Recruitment by country and center	Randomized	Yes	Yes
Demographic characteristics	Randomized	Yes	Yes
Background disease characteristics	Randomized	Yes	Yes
Safety			
Concomitant medications/significant non-drug therapies	Safety	Yes	Yes
All adverse events and Serious adverse events (including narratives)	Safety	Yes	Yes
General, liver, and renal specific safety laboratories (categorical analysis)	Safety	Yes	Yes
ECG (Categorical analysis)	Safety	Yes	Yes
Vital signs (clinical notable)	Safety	Yes	Yes
Early treatment failures	Safety	Yes	Yes
Efficacy			
PCR corrected and uncorrected cure rates at Day 29	Per-Protocol	No	Yes
PCR corrected and uncorrected cure rates at Day 43	Per-Protocol	No	Yes
PCT, FCT	FAS	No	Yes
KAF156 and LUM-SDF PK	PK	No	Yes

3 Sample size calculation

Sample size for PK run-in cohort

The objective of this part is to assess the effect of LUM-SDF in the exposure of KAF156 in patients and to see if the current planned dosages for KAF156 in Part A should be modified or how to modify KAF156 dosages in Part A. Therefore, the sample size is calculated/justified based on the precision of estimating KAF156 exposure. The key variables for exposure of KAF156 are AUC_{0-24h} and C_{max} . It's well known that the distribution of AUC or C_{max} is best described by log normal distribution. The half width of 2-sided 90% confidence interval for the log AUC_{0-24h} or log C_{max} is the target for sample size calculation. The relevant historical data for sample size calculation are the standard deviations of log AUC_{0-24h} and log C_{max} , which are usually invariant to the dosage.

In POC Study X2202, the standard deviation for log AUC_{0-24h} was 0.26 and 0.27 for 10 *P. falciparum* patients treated with KAF156 400 mg QD 3 days and for 18 *P. falciparum* patients

treated with KAF156 800 mg QD, respectively. The corresponding standard deviation for log C_{max} was 0.205 and 0.215, respectively.

Table 3-1 Sample size and width of 2-sided 90% CI for log AUC_{0-24h} and log C_{max}

Standard deviation (in log)	n	Target half width of 2-sided 90% CI	Probability that observed half width of 2-sided 90% CI is ≤ the target
0.21	9	0.153	0.80
0.21	12	0.126	0.80
0.21	10	0.150	0.80
0.26	9	0.200	0.80
0.26	12	0.155	0.80
0.26	13	0.150	0.80
0.26	12	0.150	0.70
0.27	9	0.200	0.80
0.27	12	0.161	0.80
0.27	14	0.150	0.80
0.27	12	0.150	0.68

Based on nQuery Table MOC1-1.nqa.

A sample size of 12 patients will provide 80% probability that the observed half width of 2-sided 90% CI for log AUC_{0-24h} is ≤0.155. A sample size of 12 patients will provide 80% probability that the observed half width of 2-sided 90% CI for log C_{max} is ≤0.126.

Part A

The primary efficacy objective for this part is to determine the effective dose(s) of KAF156 combined with LUM-SDF for treatment of uncomplicated malaria caused by *P. falciparum* in adolescents and adults. The primary efficacy endpoint is the PCR corrected ACPR rate at Day 29 based on the per-protocol analysis set. The statistical null hypothesis is that the ACPR rate is at most 80% with the alternative hypothesis that the ACPR rate is greater than 80%. The statistical hypothesis will be evaluated using the lower limit of 2-sided 95% exact confidence interval for the ACPR rate. If the lower limit of 2-sided 95% exact confidence interval for ACPR rate is greater than 80%, the null hypothesis will be rejected.

Rejecting the null hypothesis of at most 80% ACPR rate is equivalent to showing non-inferiority to a ACPR rate of 90% with a non-inferiority margin of 10%. 90% is specified in the [2015 WHO guidelines](#) as the ACPR rate cutoff-threshold for a change in treatment policy and a 10% non-inferiority margin is considered as acceptable for early-phase trials ([Held, et al 2015](#)).

[figure not shown]
[Figure 3-1](#) plots the power to reject the null hypothesis of at most 80% ACPR rate versus sample size by various true ACPR rates (90%, 93%, 95%, and 97%). Due to the discrete property of binomial distribution, the power increases zigzag with jump at 26, 34, 41, 48, 55, 62, and 68 as the sample size increases. When the sample size is at least 41, the power to reject the null hypothesis of at most 80% ACPR rate is about 80% or higher if the true rate is 95% or higher.

Since there is a 2:1 ratio among different treatment groups, the sample size in the per-protocol analysis set will be targeted to be 42 patients for each KAF156/LUM-SDF dose combination

group and 21 patients for the comparator (Coartem[®]) cohort. This sample size will provide at least 80% power to reject the null hypothesis of at most 80% ACPR rate for the 6 KAF156 dose combinations if the true ACPR rate is at least 95%. If there are multiple KAF156/LUM-SDF dose combinations that are all effective, the less frequent or/and highest KAF156/LUM-SDF dose combination(s) that is tolerable may be selected for further evaluation. The PK/PD modeling may be used to assist the selection of appropriate dose combination(s) for Part B.

Assuming that about 16% of patients will be excluded from the per-protocol analysis set, about 325 patients (50:50:50:50:50:25) will be randomized to yield 42 patients for each KAF156/LUM-SDF dose combinations and 21 patients for the Coartem[®] cohort in the per-protocol analysis set.

Figure 3-1 Power to reject adequate clinical and parasitological response (ACPR) rate less than or equal to 80% based on 2-sided 95% CI by true rate

Part B

The primary objective for this part is to assess the safety and efficacy of the selected KAF156/LUM-SDF dose combination(s) adjusted for body weight in pediatric patients. For the primary efficacy variable of PCR corrected ACPR rate at Day 29 based on the per-protocol analysis set, a sample size of at least 41 patients will provide about 80% power or higher to reject the null hypothesis of at most 80% ACPR rate based on the lower limit of 2-sided 95% exact confidence interval if the true rate is 95% or higher for a KAF156/LUM-SDF dose combination. Since there is a 2:1 ratio between a KAF156/LUM-SDF dose combination group and the Coartem[®] cohort, the sample size in the per-protocol analysis set will be targeted to be 42 patients for each KAF156/LUM-SDF dose combination group and 21 patients for the Coartem[®] cohort. Assuming that 16% of patients will be excluded from the per-protocol analysis set, about 50 pediatric patients will be randomized to yield 42 patients for each KAF156 and LUM-SDF combination and 21 patients for the Coartem[®] cohort in the per-protocol analysis set.

4 Change to protocol specified analyses

None

5 Appendix

